3.7. Data Monitoring Committee

An independent DMC will be responsible for monitoring safety data from the study. For Cohorts 1 and 2, the DMC met after all evaluable subjects in the dosing cohort completed Week 12 of the study to review the safety data and provided their recommendation for progressing to the next dosing cohort or enrollment of subjects into additional cohorts. So far, DMC has reviewed safety data up to Week 52 for Cohorts 1-3 and Week 24 for Cohort 4; there were no safety concerns from the DMC and the recommendation has been to continue the study. The DMC will meet at the end of the study and may, at any time, recommend modifying or pausing enrollment due to safety concerns based on their periodic data reviews.

Enrollment will be paused, and the DMC and regulators will be notified if, at any time during the study, any of the events listed below occur following administration of DTX401:

- Death of a subject
- An event with an intensity ≥Grade 3 (according to the National Cancer Institute Common Terminology Criteria for Adverse Events) develops
- Occurrence of a hepatic malignancy

If a stopping rule is met, enrollment will be paused, and the DMC will meet to review available data. If a decision is made to resume enrollment, this decision will be communicated to and, if required, approved by regulatory authorities according to country requirements.

4. STUDY ENDPOINTS AND COVARIATES

The full schedule of assessments is shown in Appendix 1.

4.1. Primary Endpoint(s)

The incidence of adverse events (AEs), including the incidence of DLTs at each dose level, treatment-emergent adverse events (TEAEs), and serious adverse events (SAEs) for each dosing cohort, assessed by severity and relationship to study product. Specifically,

[figure not shown]
- TEAEs by SOC and PT
- DLTs by SOC and PT
- Related TEAEs by SOC and PT
- Serious TEAEs by SOC and PT
- Serious Related TEAEs by SOC and PT
- TEAEs by PT and greatest severity

4.2. Secondary Endpoint(s)

- The change from baseline in time (in minutes) to first hypoglycemic event (defined as glucose <54 mg/dL [<3.3 mmol/L])* during a controlled fasting challenge at 12, 24, and 52 weeks after IV administration of DTX401.
 - * Following protocol amendment 6, the definition of euglycemia for the end of the controlled fasting challenge changed from \geq 60 mg/dL (\geq 3.3 mmol/L) to \geq 54 mg/dL (\geq 3.0 mmol/L

4.3. Exploratory Endpoints

5. **DEFINITIONS**

5.1. Baseline

Baseline is defined as the last non-missing assessment taken prior to the dose of DTX401, unless specified otherwise.

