	
appropriate care and use of the CGM device and sensors, and instructed to wear the CGM device through the Week 52 visit or early withdrawal.
 
Day 0 – Baseline Assessments
 
Subjects will be admitted to the study site or hospital on Day 0 and discharged approximately 24 hours after administration of DTX401 (on Day 2). Each subject will remain on his or her prescribed diet for the duration of the inpatient stay. A blood sample for measurement of lipid levels will be collected on the morning of hospital admission. The sample should be collected at least 2 to 4 hours after the subject’s last meal.
 
A urine pregnancy test will be administered (for females of childbearing potential only). Blood samples will be collected for clinical laboratory assessments (clinical chemistry [including liver function tests], hematology, and coagulation panel), AAV8 neutralizing antibody testing, AAV8 binding antibody IgG testing, cell-mediated immune response to AAV8 and G6Pase testing, and anti-G6Pase antibody testing. A urine sample will be collected for urinalysis. Saliva, urine, and stool samples will be collected to provide a baseline for assessment of vector shedding. A 12-lead ECG and a targeted physical examination will be performed. Vital sign measurements and weight will be recorded. Adverse events and SAEs will be monitored. The number of symptomatic hypoglycemic events with documented glucose of < 60 mg/dL (< 3.0 mmol/L) that occurred since the last visit; concomitant medications, therapies, and procedures; and the subject’s daily prescribed diet, daily diet intake, daily prescribed cornstarch (or equivalent), and daily cornstarch (or equivalent) intake will be recorded.
 
Subjects will complete the [REDACTED] prior to invasive assessments being conducted. Subjects will complete the GSDIa Morning Diary and GSDIa Evening Diary daily for 7 days leading up to and including the Day 0 visit.
 
Subjects will participate in a controlled fasting challenge. The Investigator or delegated sub-investigator will review the results of all laboratory assessments performed on the first day of the inpatient visit, including morning cortisol. Subjects should wear their CGM device throughout the fasting challenge, and should not change the sensor prior to the assessment. Before the controlled fasting challenge begins, the study site will provide dinner for the subject. The dinner meal will be personalized for each subject and will include a target carbohydrate range and overall composition in protein, fats and dietary fibers that is as close as possible to the subject’s most current dinner dietary prescription. The content of the dinner and quantities consumed will be recorded.
 
After dinner, subjects will be given an oral dose of cornstarch equivalent per their most recent cornstarch prescription at approximately the same time that they typically take it, but no later than 3 hours post dinner. The time of ingestion of prefasting cornstarch and the amount consumed will be recorded. After the cornstarch is ingested, the controlled fasting challenge will begin, and the start time will be recorded accordingly. If subjects do not receive cornstarch overnight, or receive continuous overnight feedings, the fasting test will begin after they complete their dinner. Subjects will be instructed to minimize activity after they finish eating dinner until the end of the fasting challenge.
 
During the fast, subjects may not ingest any food or drink other than water. The controlled fasting challenge will end when the subject’s glucose level decreases to < 54 mg/dL (< 3.0 mmol/L) or when the subjects present signs and symptoms of hypoglycemia, or the fast reaches 15 hours without hypoglycemia, whichever occurs first. The stop time of the controlled fasting challenge will be recorded. At the end of the controlled fasting challenge, the subject’s hypoglycemia should be treated per the institution’s standard procedure, which may include providing the subject with a meal, cornstarch, or IV glucose, if medically indicated.
 
Blood samples for measurement of cortisol, fatty acid, glucagon, insulin, C-peptide, growth hormone, insulin-like growth factor-binding protein 1 (IGFBP1), alanine and ketone levels

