--	---

will be collected at the beginning and end of the fasting challenge, or more frequently at the Investigator’s discretion. A final sample for glucose, lactate, growth hormone, IGFBP1, ACTH, and cortisol measurement will be collected 30 minutes after the end of the controlled fasting challenge. Samples should be prepared and transported to the local laboratory in accordance with the site’s standard procedures. Blood samples for STAT analysis of glucose and lactate will be collected per the schedule of events. Capillary glucose will also be assessed.
 
Urine will be collected over 24 hours for the determination of total protein, microalbumin, and creatinine. The collection of urine can overlap with the controlled fasting challenge. A [REDACTED] will be performed after the controlled fasting challenge is complete.
 
For subjects enrolled in Cohort 4, the Investigator will initiate a prophylactic steroid regimen after completion of the controlled fasting challenge (Section 8.2.6.2.2).
 
Day 1 – DTX401 Infusion
 
Subjects will receive a single IV infusion of DTX401. The start of the DTX401 infusion should be after all samples and procedures specified for Day 1 predose have been completed. Subjects will be discharged after a 24-hour observation period.
 
Prior to dosing with DTX401, blood samples will be collected for clinical chemistry (including liver function tests) and vector genome determination. A 12-lead ECG will be performed, and vital sign measurements will be recorded. Adverse events and SAEs will be monitored. The number of symptomatic hypoglycemic events with documented glucose of < 60 mg/dL (< 3.3 mmol/L) and concomitant medications, therapies, and procedures will be recorded.
 
After dosing with DTX401, a blood sample will be collected approximately 22 hours after the start of the infusion for clinical chemistry (including liver function tests) and vector genome determination. Vital sign measurements will be recorded approximately 5 minutes after the start of the infusion and approximately 0.5, 1, 4, 8, and 22 hours after the start of the infusion. Adverse events and SAEs will be monitored. The number of symptomatic hypoglycemic events with documented glucose of < 60 mg/dL (< 3.3 mmol/L) and concomitant medications, therapies, and procedures will be recorded. At the end of the visit, the Morning Glucose Level monitoring worksheet and instructions for completing it will be provided to the subject (Section 8.1.3).
 
Subjects in Cohort 3 will be discharged with prednisone to allow rapid treatment of possible vector-induced hepatitis if it occurs following treatment with DTX401 (Section 8.2.6.2.1). Subjects in Cohort 4 will be discharged with prednisone per the prophylactic steroid regimen (Section 8.2.6.2.2).
 
Outpatient Study Site or Home Visits
 
Subjects will be asked to provide clinical laboratory samples at a minimum of every 3 to 4 days through Week 12 of the study, or longer if clinically indicated. Subjects may have the option of having these samples collected at their homes by clinically trained and qualified personnel (if arranged by the Investigator), unless there is a scheduled study site visit that the subject must attend in person.
 
A blood sample will be collected for determination of clinical chemistry (including liver function tests) and sent to the central laboratory. A second blood sample will be collected for liver function tests and sent to the local laboratory (STAT sample). A blood sample will be collected for determination of cell-mediated immune response to AAV8 and G6Pase testing approximately weekly.
 
Saliva, urine, and stool samples will be collected for assessment of vector shedding until at least 3 consecutive negative results are obtained from each sample matrix.

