### **3.2.2.2. Baseline Visit – Day 1**

The assessments and procedures to be performed on Day 1 are listed in the Schedule of Events (Table 6).

Following completion of the Day 0 assessments (ie, controlled fasting challenge and 24-hour urine collection), subjects will receive a single, peripheral IV infusion of DTX401. Safety (vital sign measurements [Section 8.2.1], clinical laboratory assessments [Section 8.2.6], and AEs and SAEs [Section 9.1]) will be monitored over 24 hours following infusion of DTX401 (Table 6). Any AEs that occur during this 24-hour observation period will be treated with appropriate supportive and medical care deemed necessary for the well-being of the subject.

Subjects will be discharged after a 24-hour observation period. Subjects in Cohort 3 will be discharged with prednisone to allow rapid treatment of possible vector-induced hepatitis if it occurs following treatment with DTX401 (Section 8.2.6.2.1). Subjects in Cohort 4 will be discharged with prednisone per the prophylactic steroid regimen (Section 8.2.6.2.2).

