***Laboratory sample collection before and during the controlled fasting challenge***

On the morning of inpatient visit for the controlled fasting challenge, after vital signs and other non-interventional assessments have been performed, samples will be collected for standard clinical chemistry (including lipid levels), hematology, coagulation panel, and urinalysis. These samples should be collected at least 2 to 4 hours after the subject's last meal prior to admission and sent to the central lab. A sample for STAT AST and ALT level analysis will also be collected at this time and sent to the local laboratory; the Investigator or delegated subinvestigator should review the results before starting the controlled fasting challenge.

All subjects should have a morning cortisol and ACTH measurement prior to their baseline fasting challenge. Cortisol and ACTH results should be reviewed by the Investigator or delegate before starting the fasting challenge. Abnormal morning cortisol results might require postponing the fasting challenge until further HPA axis testing is performed.

For subjects with suspected HPA axis dysfunction (eg, after prolonged steroid treatment) supplemental tests can be conducted (eg, stimulation tests) before deciding if it is safe to conduct the fasting challenge. In most cases, morning cortisol and supplemental tests will be conducted one week prior to the visit. It is also possible to perform these tests at the site on Day 1 of the visit under the conditions that all results will be available prior to the beginning of the CFC.

Total urine voided over the 24-hour period starting at the time of inpatient admission will be collected during the controlled fasting challenge.

Blood samples for measurement of cortisol, ACTH, free fatty acids, glucagon, insulin, C-peptide, growth hormone, IGFBP1, alanine and ketone levels (3-hydroxy butyrate) will be collected at the beginning (ie, immediately after the post-dinner dose of cornstarch, or immediately after dinner for subjects who do not take a post-dinner dose of cornstarch) and end of the controlled fasting challenge, or more frequently at the Investigator's discretion. A final sample for glucose, lactate, growth hormone, IGFBP1, ACTH and cortisol measurement will be collected 30 minutes after the end of the controlled fasting challenge. Samples should be prepared and transported to the local laboratory in accordance with the site's standard procedures.

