**8.2.6.2.2. Prophylactic Steroid Treatment for Vector-Induced Hepatitis**

Subjects in Cohort 4 will receive prophylactic oral steroid treatment to prevent possible vector-induced hepatitis. Prophylactic oral steroid regimens have been used in AAV-mediated gene transfer clinical trials for other indications (eg, Clinicaltrials.gov identifiers: NCT03223194, NCT03306277).

Oral prednisone (or prednisolone) will be initiated on Day 1 following completion of the Day 0 controlled fasting challenge and before DTX401 administration as follows:

█ [REDACTED]

█ [REDACTED]

█ [REDACTED]

█ [REDACTED]

█ [REDACTED]

█ [REDACTED]

█ [REDACTED]

█ [REDACTED]

[REDACTED]

The Investigator, in conjunction with the Ultragenyx medical lead, may consider modifying this regimen if a subject's ALT levels do not normalize during the steroid taper.

Additional oral prednisolone/placebo may be administered after completion of the taper if a subject's alanine aminotransferase (ALT) levels increase from Baseline and/or above the ULN of recently drawn levels repeated one more time as soon as possible.

[REDACTED]

[REDACTED]

If, in the Investigator's medical judgment, the subject may not safely tolerate initiation of oral steroid treatment on Day 1, the steroid regimen may be modified based on discussion between the Investigator and the Ultragenyx medical lead. The Investigator should document the agreed upon steroid regimen in the subject's source documentation.

The Investigator may consider additional assessments or medical care, such as hospitalization or daily clinic visits, during steroid administration if, in the Investigator's medical judgment, these measures would provide additional safety benefits.

The use of prednisone will be recorded on the appropriate page of the eCRF.

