- k A blood sample for measurement of lipid levels will be collected on the morning of hospital admission for each controlled fasting challenge at approximately the same time starting at Day 0. The sample should be collected at least 2 to 4 hours after the subject's last meal.
- l A blood sample for determination of clinical chemistry (including LFTs) will be collected approximately 22 hours after the start of DTX401 infusion.
- m Blood samples for measurement of cortisol, fatty acid, glucagon, insulin, C-peptide, growth hormone, IGFBP1, ACTH, alanine, and ketone levels will be collected at the beginning and end of each controlled fasting challenge, or more frequently at the Investigator's discretion.
- n If possible, a blood sample for measurement of ACTH and cortisol levels will be collected approximately 1 week before the Week 12 visit.
- o It is recommended that the Screening sample for AAV8 neutralizing antibody testing be collected at the time written informed consent is provided.
- p A blood sample for vector genome determination will be collected approximately 22 hours after the start of DTX401 infusion.
- q [REDACTED]
- r The subject's daily prescribed diet and daily diet intake will be recorded at the time points specified in [Table 6](#) and, if possible, on a weekly basis through the Week 52 visit or early withdrawal.
- s The subject will remain on his or her prescribed diet for the duration of each inpatient study visit.
- t The subject's daily prescribed cornstarch (or equivalent) and daily cornstarch (or equivalent) intake will be recorded at the time points specified in [Table 6](#) and, if possible, on a weekly basis through the Week 52 visit or early withdrawal.
- u Supplemental information on glucose level trends will be collected using a CGM device. The site will provide a CGM device to the subject during the Screening Period after determining that the subject is eligible for the study. Subjects will be educated on the appropriate care and use of the CGM device and sensors, and instructed to wear the CGM device through the Week 52 visit or early withdrawal. Data from the subject's CGM device will be transferred to the Sponsor throughout the study, including a final data transfer at the end of the Week 52 visit or early withdrawal.

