8.6.7. Clinical Laboratory Assessments

Clinical laboratory assessments are mainly collected at central laboratory (Table 2), except for data collected during CFC which is collected at local laboratory and analyzed as described in Section 8.5.1. For all central clinical laboratory parameters (Table 2) with continuous results, absolute values and changes from baseline will be summarized by study visit. For central laboratory parameters with categorical results, results will be included in a listing because these parameters are either non-critical for analysis (e.g., Urinalysis blood (by dipstick), or microscopic examination parameters, etc.) or they are collected only at screening visit (e.g., HBV surface antigen).

Listings of laboratory parameters will be provided. Individual patient profile of triglyceride with daily cornstarch intake over time will be plotted.

Table 2: Central Clinical Laboratory Parameters

Clinical chemistry:	Lipid panel, uric acid, sodium, potassium, chloride, carbon dioxide, blood urea nitrogen, creatinine, glucose, calcium, phosphate, magnesium, albumin, total protein, creatine kinase, bilirubin (total, direct, and indirect), ALT, AST, ALP, gamma-glutamyl transferase, and lactate dehydrogenase
Hematology:	Complete blood count with differential
Urinalysis:	Specific gravity, pH, glucose, protein, blood (by dipstick), ketones (by dipstick), and microscopic examination (if blood or protein is found)
Other:	HBV surface antigen, HCV RNA, HIV,
(collected only at Screening)	
Coagulation panel:	PT/INR, aPTT
24-Hour urine:	Total protein, microalbumin, and creatinine

Abbreviations: ALP = alkaline phosphatase; ALT = alanine aminotransferase; aPTT = activated partial thromboplastin time; AST = aspartate aminotransferase; HBV = hepatitis B virus; HCV = hepatitis C virus; HIV = human immunodeficiency virus; PT/INR = prothrombin time/international normalized ratio.

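### The SAP baseline rule selects the Day 1 predose chemistry sample instead of the Day 0 admission sample, so changes in glucose, uric acid and possibly lipids at the inpatient visits are not like-for-like

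*SAP*

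**What the plan says.** SAP 5.1 gives one general rule: "Baseline is defined as the last non-missing assessment taken prior to the dose of DTX401, unless specified otherwise". SAP 8.6.7 says that for continuous central laboratory parameters "absolute values and changes from baseline will be summarized by study visit", and it names no other baseline. SAP Table 2 places the lipid panel, uric acid, glucose and liver enzymes under clinical chemistry.

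The protocol schedules two chemistry draws around admission.

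- **Day 0** (Synopsis, baseline assessments): "Blood samples will be collected for clinical laboratory assessments (clinical chemistry [including liver function tests], hematology, and coagulation panel), AAV8 neutralizing antibody testing". Section 8.1.1 puts this draw on the morning of admission, before the challenge, and sets a meal interval: "These samples should be collected at least 2 to 4 hours after the" last meal. The same instruction governs each inpatient challenge visit. A Schedule of Events footnote adds that the lipid sample "will be collected on the morning of hospital admission for each controlled fasting challenge at approximately the same time starting at Day 0".
- **Day 1** (Synopsis, infusion day): "Prior to dosing with DTX401, blood samples will be collected for clinical chemistry (including liver function tests) and vector genome determination".

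On the order of events, Section 3.2.2.2 states: "Following completion of the Day 0 assessments (ie, controlled fasting challenge and 24-hour urine collection), subjects will receive a single, peripheral IV infusion of DTX401". For Cohort 4, Section 8.2.6.2.2 states: "Oral prednisone (or prednisolone) will be initiated on Day 1 following completion of the Day 0 controlled fasting challenge and before DTX401 administration".

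**The concern.** A change from baseline is easiest to interpret when both values are taken under the same conditions. The protocol arranges this for the inpatient visits: chemistry is drawn on the morning of admission with a minimum meal interval, and lipids at about the same clock time as on Day 0. The SAP rule passes over the Day 0 sample that was collected to match and substitutes one for which no meal condition is given.

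Glucose, uric acid and lipids are the metabolic markers of this disease, and they are sensitive to recent fasting and feeding. If the baseline carries an acute effect of the challenge or its treatment, the reported change mixes that effect with the effect of DTX401. Cohort 4 raises a further question. Its baseline may be post-steroid, while Cohorts 1 to 3, on reactive regimens, have no protocol steroid before dosing. SAP 8.1 presents summaries by cohort.

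**Working it through.** No figure in the plan needs reproducing. The check applies the rule to the scheduled draws and then places the selected sample in time.

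**Step 1: which sample the rule selects** (draws from the protocol Synopsis)

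| Parameter group | Scheduled predose draws | Baseline under SAP 5.1 |
|---|---|---|
| Clinical chemistry | Screening, Day 0, Day 1 predose | Day 1 predose |
| Hematology | Screening, Day 0 | Day 0 |
| Coagulation | Screening, Day 0 | Day 0 |
| Urinalysis | Screening, Day 0 | Day 0 |
| 24-hour urine | Day 0 | Day 0 |

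Only chemistry moves to Day 1. The Synopsis text is enough to show this; the incomplete schedule table is not needed for it.

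**Step 2: when the challenge ends**

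Inputs from the documents: cornstarch 0 to 3 h after dinner and a 15 h cap on the fast (protocol 3.2.2.1); cited fasting times with cornstarch of median 7 h and up to 10 h (protocol 1.3.1). Assumption, not in the documents: dinner ends between 17:00 and 20:00.

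End of challenge = end of dinner + delay to cornstarch + length of fast.

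- 7 h fast: 17 + 0 + 7 = 24 (00:00) to 20 + 3 + 7 = 30 (06:00 on Day 1).
- 10 h fast: 17 + 0 + 10 = 27 (03:00) to 20 + 3 + 10 = 33 (09:00 on Day 1).
- 15 h cap: 17 + 0 + 15 = 32 (08:00) to 20 + 3 + 15 = 38 (14:00 on Day 1). The subject is then up to 3 + 15 = 18 h past dinner.

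Infusion comes after the challenge is complete, and hypoglycemia at its end may be treated with a meal, cornstarch or IV glucose. A predose draw on Day 1 therefore normally falls after the fast and any treatment or, at the extreme, late in the fast. No passage times the draw against the end of the challenge, so this is an inference from the sequence.

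**Step 3: how a shift enters the analysis**

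Let B0 be the Day 0 value, B1 the Day 1 predose value and Y the value at a later visit.

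- Change under the SAP rule: Y − B1 = (Y − B0) − (B1 − B0).
- The term (B1 − B0) enters in full and is the same at every post-dose visit for that subject.
- With 3 subjects per cohort, a shift of size s in one subject moves the cohort mean change by s/3.

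The documents contain no predose laboratory values, so s cannot be estimated.

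**Step 4: how the documents use the word baseline**

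Protocol exclusion criterion 1 and Sections 8.2.3, 8.2.6.3 and 8.2.6.4 attach Baseline to Day 0. Section 8.2.3 lists the Day 1 predose ECG separately from it. The Schedule of Events has a baseline column for Day 0 and places Day 1 predose under dosing. The heading of Section 3.2.2.2 points the other way, since it calls Day 1 a baseline visit. SAP 8.5.1 names Day 0 for the fasting challenge, so parameter-specific baselines are already part of the SAP's practice.

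**The case against.** The last value before dose is a conventional safety baseline, and the analyses are descriptive (SAP 8.6). No test, dose decision or MTD estimate depends on them. Absolute values by visit and listings are planned, so both predose values should remain visible. All of this stands, and it limits the weight of the point.

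The Day 1 sample may also be less different than it looks. The 24-hour urine collection starts at admission and must finish before infusion, so dosing comes about 24 h or more after admission. After a 7 h fast the subject could have been treated and fed hours before the draw. This also stands: a mismatch in metabolic state is not documented for any individual subject. It does not restore the matching, because the Day 1 interval since food is not stated at all.

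Three stronger readings are tempting, and the documents do not support them.

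- *The glucose baseline falls by more than 6 mg/dL.* A reader might subtract the challenge stopping threshold (54) from the eligibility threshold (60). These are limits that apply to different samples. The end-of-challenge glucose is a local STAT result outside the central analysis, and glucose after treatment would no longer sit at the threshold. The 54 mg/dL stop came with Amendment 6, which was prompted by Cohort 2 and 3 results through Week 52. The baseline challenges of Cohorts 1 to 3 (9 of the 12 planned subjects) therefore preceded it.
- *The lipid matching is certainly undone.* The lipid footnote mentions only the admission sample, while Table 2 puts the lipid panel inside chemistry. If no predose lipid value exists, the rule already returns Day 0.
- *All laboratory changes at all visits are affected.* Step 1 shows that only chemistry is. Outpatient and home draws have no stated meal condition, so neither baseline matches them.

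**Conclusion.** The point holds for central clinical chemistry at the inpatient visits. As written, SAP 5.1 with 8.6.7 makes the Day 1 predose sample the baseline, while the admission samples at Weeks 12, 24 and 52 follow Day 0 conditions. Week 12 counts here only when it is held as an inpatient visit. Change from baseline in glucose, uric acid and, if run predose, lipids is then not like-for-like.

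The size and direction of the shift are unknown. The conclusion rests on two inferences: that the Day 1 sample follows the challenge and any treatment, which the order of events makes the normal case, and that in Cohort 4 it may follow the first prednisone dose. A reader might infer that the Cohort 4 baseline is definitely post-steroid. The documents do not say so, because they order both events before infusion but not against each other.

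The fasting-challenge endpoint is unaffected because SAP 8.5.1 names Day 0. This is a worthwhile correction to a descriptive analysis and does not threaten the trial's main conclusions.

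**What to change.** In SAP 5.1 or 8.6.7, add that for meal- and steroid-sensitive central chemistry (glucose, uric acid, lipid panel) baseline is the Day 0 admission sample drawn before the fasting challenge. If that value is missing, use the last non-missing predose value and flag it. Falling back to Screening would be worse, since that value can be up to 56 days older than Day 0. Report Day 1 predose as its own time point in the by-visit tables.

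Liver tests may stay on the last-predose rule, since nothing in the documents shows that the challenge or its treatment disturbs them.

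The cost is one SAP sentence and a small programming change, with no new data. The downside is that the conventional last-predose baseline is given up for these parameters, so chemistry will have two baseline definitions, which table footnotes should state.
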